- The proportion of participants who, at week 6, according to the investigator's assessment on the GAIS score, have achieved a score of 1 or higher (improved, much improved, or very much improved).
- Changes from baseline in waist circumference at weeks 6 and 12 using a flexible measuring tape.
- Changes from baseline in body weight at weeks 6 and 12.
- Changes from baseline in right and left thigh circumference at weeks 6 and 12 using a flexible measuring tape.
- Changes from baseline in flank fat on each side measured by caliper at weeks 6 and 12.
- Assessment of the trend in dermal and hypodermal thickness changes on both sides by measurement with ultrasonography from baseline to weeks 6 and 12
- Assessment of participants' satisfaction at weeks 6 and 12
- Assessment of the incidence of AEs following treatment

Section 3: Research Methods

Study Design

This is a single- arm, open-label clinical trial evaluating the efficacy and safety of Embella® (Deoxycholic acid, produced by Espad Pharmed Darou Company) for the treatment of flank fat

Randomization

There is no randomization.

Blinding

The study is an open-label clinical trial.

Sample size

In this study, 30 participants will be enrolled.

Study Population Criteria

Inclusion Criteria

1. Men and women aged between 21 and 65 years

2. Presence of mild to moderate flank fat, as assessed by the investigator and ultrasound and/or caliper (with a thickness of ≥ 2 cm of adipose tissue at the posterior axillary lines at the level of the ASIS).
3. Signing of the informed consent form by the participants
4. Ability to comply with study instructions and likelihood of completing all required visits
5. Agreement to abstain from any treatment in the flank area, including botulinum toxin, hyaluronic acid fillers, cosmetic surgery, laser/light therapy, chemical peels, etc., throughout the study period.

Exclusion Criteria

1. Planning for lifestyle modification during the predicted duration of the study
2. History of liposuction or laser lipolysis surgery within the past 12 months, or intention to undergo these procedures
3. Significant weight loss in the past 6 months or planned weight loss during the anticipated duration of the study
4. Body mass index (BMI) greater than 30 kg/m^2
5. Waist circumference greater than 105 centimeters
6. Affliction with uncontrolled systemic diseases
7. Severe cardiovascular diseases
8. Known hypersensitivity or allergy to the study product or its components
9. Pregnant women, breastfeeding women, or women who are expected to become pregnant during the anticipated duration of the study
10. Current enrollment in a drug or investigational device study, or participation in such a study within the past 30 days, as well as during the course of the study.
11. Previous treatment of the flank area with hyaluronic acid fillers or semi-permanent fillers within the past 12 months
12. Use of permanent fillers or silicone in the flank area

13. Individuals who intend to undergo cosmetic procedures in the treatment area during the study, or who have a history of cosmetic procedures (such as surgery) or visible scars in that area that may affect the assessment.
14. Individuals with volume loss due to trauma, adipose tissue disorders associated with autoimmune diseases such as generalized lipodystrophy (e.g., in juvenile dermatomyositis), localized lipodystrophy (such as Barraquer-Simons syndrome), hereditary diseases, or HIV-associated disease
15. Infection or skin diseases at the injection site
16. Evidence of recent alcohol or drug abuse
17. Medical and/or psychiatric conditions of such severity that they may interfere with the outcomes of the study
18. Having a known bleeding disorder or the use of medications that increase the likelihood of bleeding after injection
19. Presence of hair in the flank area that interferes with assessment or treatment
20. Predisposition to hypertrophic scar formation
21. History of anaphylaxis or allergy to lidocaine (or other amide anesthetics), hyaluronic acid products, or streptococcal proteins
22. Affliction with Porphyria
23. Presence of active inflammation, infection, malignant or premalignant lesion, or non-healed ulcer in the flank region
24. Having a condition or being in a situation which, in the opinion of the investigator, may place the individual at significant risk, disrupt the study results, or interfere with the individual's participation in the study.

Withdrawal Criteria

1. Withdrawal of participant from informed consent
2. Non-compliance, including refusal to adhere to the medical requirements of the study, failure to undergo procedures specified in the study protocol, or use of prohibited medications.

3. Inability to follow up on the participant's status
4. Treatment of the flank area with hyaluronic acid fillers or semi-permanent fillers during the course of the study
5. The use of any permanent filler or silicone materials in the flank area during the course of the study
6. Undergoing any cosmetic procedures in the treatment area during the study period (such as surgery)
7. Having conditions that, in the opinion of the investigator, may interfere with the assessment of efficacy

Section 4: Outcome Variables

Primary Outcomes

The proportion of participants who, at week 12, according to the investigator's assessment on the GAIS score, have achieved a score of 1 or higher (improved, much improved, or very much improved).

Secondary Outcomes

- The proportion of participants who, at week 6 based on the investigator's assessment on the GAIS score, have achieved a score of 1 or higher (improved, much improved, or very much improved).
- Changes from baseline in waist circumference at weeks 6 and 12 using a flexible measuring tape.
- Changes from baseline in body weight at weeks 6 and 12.
- Changes from baseline in right and left thigh circumference at weeks 6 and 12 using a flexible measuring tape.
- Changes from baseline in flank fat on each side measured by caliper at weeks 6 and 12.
- Assessment of the trend in dermal and hypodermal thickness changes on both sides by measurement with ultrasonography from baseline to weeks 6 and 12
- Assessment of participant satisfaction at weeks 6 and 12
- Assessment of the incidence of AEs following treatment

Section 5: Descriptive statistics

Baseline characteristics

Baseline characteristics	Categories
Age	-
Sex	Male/Female

Descriptive statistics for baseline characteristics will be presented as mean and standard deviation for continuous variables, and as frequency and percentage for categorical variables.

Section 6: Statistical Analysis

This section describes the planned statistical analyses for efficacy and safety outcomes. Results will be summarized using appropriate descriptive statistics and analyzed using suitable statistical models depending on the data type. Treatment effects will be presented with 95% confidence intervals and two-sided p-values, using a significance level of 0.05.

Study Profile

All participants who sign the informed consent form will be included in the final statistical report. The participants flow throughout the study, reasons for withdrawal from the study, and major deviations and violations of the protocol will be reported.

Statistical Software

The analysis will be carried out using R statistical software.

Missing Data

No imputation will be done.

Outlier data

Outliers are identified by examining standard charts, and those that are visually "distinct" are evaluated to check the impact on the results by comparing the results of the analysis with and without outliers.

Data Transformations

No transformations of raw data are planned prior to statistical analysis. All variables will be analyzed using their original measurement scales, unless transformation is deemed necessary during model diagnostics. In such cases, justification and details will be documented in the statistical outputs and Clinical Study Report (CSR).

Multiple comparisons and multiplicity

No formal procedures for multiplicity adjustment are planned for this study, as the study was not designed to perform multiple statistical comparisons for primary or key secondary endpoints. Therefore, the overall Type I error rate will not be adjusted.

Primary Endpoint Analysis

Participants who, in the GAIS score assessment by the investigator, received a score of 1 or higher will be reported with the number and percentage.

Secondary Endpoint Analysis

Descriptive analysis of data for quantitative variables will be reported as mean and standard deviation (SD) or median and interquartile range (IQR), based on the data distribution, and for qualitative variables as the number and percentage. Changes over time will be analyzed using repeated measures analysis of variance (repeated measures ANOVA) or the Friedman test, depending on the data distribution. Comparisons between baseline and subsequent timepoints will also be performed using the paired t-test or the Wilcoxon test, as appropriate. The significance level for the tests will be considered as 0.05.

Adverse Events' Analysis

AEs will be classified according to the MedDRA dictionary based on the Preferred Term (PT) and analyzed in terms of frequency and percentage. The severity and seriousness of each event will also be reported.

Methods used for assumptions to be checked for statistical methods

For t-test, normality of distributions will be assessed using the Shapiro-Wilk test.

References

2. Garibyan L, Sipprell WH, Jalian HR, Sakamoto FH, Avram M, Anderson RR. Three-dimensional

volumetric quantification of fat loss following cryolipolysis. *Lasers Surg Med.* 2014;46(2):75–80.

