#### **Secondary Endpoint Analysis**

Descriptive analysis of data for quantitative variables will be reported as mean and standard deviation (SD) or median and interquartile range (IQR), based on the data distribution, and for qualitative variables as the number and percentage. Changes over time will be analyzed using repeated measures analysis of variance (repeated measures ANOVA) or the Friedman test, depending on the data distribution. Comparisons between baseline and subsequent timepoints will also be performed using the paired t-test or the Wilcoxon test, as appropriate. The significance level for the tests will be considered as 0.05.

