Study Design	The present study is an interventional, single-arm, open-label study conducted in Iran, to evaluate efficacy and safety of Embella (Deoxycholic acid, produced by Espad Pharmed Co.) for the treatment of flank fat
Sponsor	Espad Pharmed Company
Principal Investigator	Investigator: [name] Affiliation: Tehran University for Medical Sciences, Department of Dermatology, Pemphigus Research Unit, Razi Hospital, Tehran, Iran
Co-investigators	[name] Tehran University of Medical Sciences, Cancer Research Center
Investigational Drug	Embella (Deoxycholic acid, produced by Espad Pharmed Co.)
Sample size	The sample size is not determined based on a statistical power calculation. 30 subjects will be studied.
Eligibility criteria	
Inclusion Criteria:
 
 1. Men and women aging between 21 to 65 years 2. Having mild to moderate flank fat assessed by the investigator and sonography and/or caliper (≥ 2cm thickness of the fat tissue in posterior axillary lines at the level of ASIS) 3. Signing informed consent by the subject 4. Ability to follow study instructions and likely to complete all required visits 5. Agreement to abstain from any treatment to the flank region, including botulinum toxins, hyaluronic acid fillers, cosmetic

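### The three-visit tests of the secondary outcomes use complete cases only and name no sphericity correction; a mixed model on all observed visits would be better

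*SAP*

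**What the plan says.** SAP Section 6 (Secondary Endpoint Analysis) gives two layers of testing for the quantitative secondary outcomes, and protocol 6.1 uses the same wording. The first is an omnibus test: "Changes over time will be analyzed using repeated measures analysis of variance (repeated measures ANOVA) or the Friedman test, depending on the data distribution". The second is pairwise: "Comparisons between baseline and subsequent timepoints will also be performed using the paired t-test or the Wilcoxon test, as appropriate". On the level, the SAP says "The significance level for the tests will be considered as 0.05".

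The outcomes are measured at baseline, week 6 and week 12, for example "Changes from baseline in waist circumference at weeks 6 and 12 using a flexible measuring tape". Body weight, thigh circumference, caliper and ultrasound thickness follow the same pattern, the last three on both sides of the body.

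On missing data the SAP says only "No imputation will be done"; the protocol has no rule. The one assumption check is "For t-test, normality of distributions will be assessed using the Shapiro-Wilk test". Neither document mentions sphericity, an epsilon correction, a mixed model, an analysis set for these tests, an expected dropout rate or a missing-data sensitivity analysis. The opening of SAP Section 6 promises that "Treatment effects will be presented with 95% confidence intervals and two-sided p-values, using a significance level of 0.05".

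**The concern.** Classical repeated-measures ANOVA and the Friedman test need a value at all three visits. With nothing imputed, one missed visit removes the participant from the omnibus test, while the paired test for the attended visit keeps that participant. One outcome can then have three different denominators.

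The week-12 paired test describes only those seen at week 12. Someone disappointed at week 6 may leave by withdrawing consent, by non-compliance or by having another procedure in the treated area, all of which are listed withdrawal reasons. The informative week-6 value is then unused in the week-12 estimate.

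Weeks 6 and 12 both follow treatment and may correlate more with each other than with baseline. That would break sphericity and make an uncorrected ANOVA p-value too small.

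These outcomes are the study's objective measurements. The design is open-label and single-arm, with an investigator rating as primary outcome, and the protocol introduction says that no single fat-measurement method can be relied on alone. The secondary estimates therefore carry weight in the interpretation.

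**Working it through.** **Inputs from the documents.** n = 30 (SAP Synopsis: "The sample size is not determined based on a statistical power calculation. 30 subjects will be studied"), k = 3 visits, nominal level 0.05. The sample size has no effect size, SD, power or dropout rate behind it, so there is no planned figure to reproduce. All dropout rates, SDs and correlations below are assumptions.

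**1. Participants retained.** Let d be the share missing at each of weeks 6 and 12. A paired test keeps 30(1 − d). The omnibus test keeps 30(1 − d)² if visits are missed independently.

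| d | Paired test | Omnibus test, independent misses |
|---|---|---|
| 5% | 28.5 | 27.1 |
| 10% | 27.0 | 24.3 |
| 15% | 25.5 | 21.7 |
| 20% | 24.0 | 19.2 |

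If participants instead leave for good after week 6, 10% dropout leaves 27 in both the omnibus and the week-12 paired test, and 30 in the week-6 paired test. The case loss thus depends on the pattern as well as the rate.

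**2. Bias in the week-12 change.** Assumed: true change −3.0 mm with SD 3.5; week-6 change with SD 3.0; correlation 0.6 to 0.8; logistic dropout on the week-6 change, with poor responders leaving more often (log-odds slope about 1 per SD, somewhat steeper for the 21% row).

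| Dropout | Completer mean (mm) | Overstatement |
|---|---|---|
| 10% | −3.18 to −3.24 | 0.18/3.0 = 6% to 0.24/3.0 = 8% |
| 17% | −3.31 to −3.42 | 10% to 14% |
| 21% | −3.43 to −3.57 | 14% to 0.57/3.0 = 19% |

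An estimate that also uses the week-6 data of those who left stays within 0.01 of −3.00. Over a wider set (dropout 10% and 20%, slopes 0.5 to 2, correlation 0.5 and 0.8) the completer mean is off by 0.02 to 0.21 SD of the change. With slope 0 the bias is nil. If good responders leave instead, the completer mean is about −2.8 to −2.5, an understatement.

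**3. Size of the uncorrected ANOVA.** The test rejects when F exceeds the 5% point of F(2, 58), which is 3.156. With sphericity epsilon e, the true size is approximately P[F(2e, 58e) > 3.156] (Box). The lower bound of e is 1/(k − 1) = 0.5.

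| e | 1.0 | 0.9 | 0.8 | 0.7 | 0.6 | 0.5 |
|---|---|---|---|---|---|---|
| Size | 5.0% | 5.6% | 6.2% | 7.0% | 7.8% | 8.6% |

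Simulation (n = 30, no true change, 40,000 data sets per covariance) agrees: 5.0% under compound symmetry, 5.4% to 5.9% under AR(1) with correlation 0.5 to 0.95, 7.5% at e = 0.60 and 8.5% at e = 0.52. In the same settings:

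- Greenhouse-Geisser ANOVA: 4.7% to 5.1%.
- Friedman: 5.5% to 6.2%, of which 5.5% already arises under compound symmetry.
- Each paired t-test: 4.8% to 5.2%.

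The bias scenario in step 2 implies e = 0.95 to 0.78, so an uncorrected size of 5.3% to 6.4%.

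**The case against.** The strongest reply is that little turns on this. The study has 30 participants, one arm and no power calculation. The primary endpoint is a count and percentage, and participant flow with withdrawal reasons will be reported, so attrition will be visible. The listed outcomes are mostly changes from baseline, which the paired tests answer at their proper level. In the scenario above the effect gives t = 3.0/(3.5/√30) = 4.7, so a size of 6% instead of 5% would not alter a conclusion. All of this stands, and it limits the point to an inexpensive improvement.

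It is also true that the mixed model is unbiased only if dropout depends on observed values. When dropout is made to depend on the week-12 change itself, the estimate using week 6 moves to −3.10 to −3.42 at 10% to 21% dropout. The plan should state that assumption.

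Three stronger readings are tempting and are not supported:

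- A reader might infer that the secondary changes in general are tested above 5%. That applies only to an ANOVA run without correction when sphericity fails. R is named without a function, so the plan is silent on correction; it does not rule one out.
- A reader might infer that the paired tests also drop anyone missing a visit. They drop a participant only for the comparison with the missed visit.
- A reader might take 185 of 221 in the cited 1.25% solution study as a dropout benchmark. The introduction says only that 185 were eligible for final evaluation, not that the other 36 dropped out.

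**Conclusion.** The point holds for the omnibus tests and for the week-12 estimate. The omnibus tests are complete-case by construction, and the week-12 comparison discards week-6 information from those who leave. The resulting bias is zero if dropout is unrelated to response. It is an overstatement of about 6% to 19% under the assumed 10% to 21% dropout among poor responders, and an understatement if good responders leave. Rate and direction are both assumptions, because the documents give neither.

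The omitted sphericity correction puts the true size of an uncorrected ANOVA anywhere from 5% to about 8.6%, depending on a covariance that is not known in advance. Only secondary endpoints are affected.

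**What to change.** In protocol 6.1 and SAP Section 6, replace the omnibus and paired tests for each quantitative secondary outcome that has a baseline with wording such as:

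> Each outcome is analysed in a linear mixed model on all observed values, with visit (0, 6, 12) as a factor, unstructured covariance within participant and Kenward-Roger degrees of freedom. Changes at weeks 6 and 12 are model contrasts with 95% confidence intervals. The number analysed at each visit is reported. Outcomes measured on both sides are modelled separately for each side. The model assumes that dropout depends only on observed values.

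Keep the paired t-test or the Wilcoxon signed-rank test as the sensitivity analysis. If repeated-measures ANOVA is retained instead, specify the Greenhouse-Geisser correction; this restores the level but does not recover incomplete participants.

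Nothing is imputed, so the missing-data rule can stay, and the contrasts supply the confidence intervals that the SAP promises and the omnibus tests do not give. The cost is one paragraph in each document and a few lines of R. The downside is slightly more modelling at n = 30: three variances and three covariances, six parameters per model, which is feasible.
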